10.6.2 Patient withdrawal from the study

A patient will be considered to have completed the main study when he or she completes the final assessment visit (Visit 12 at Week 36), after which he or she will complete the Extended Follow up up to the last visit FU10. A termination eCRF page should be completed for every patient who received study product, whether or not the patient completed the study (applicable for both main study and Extended Follow up study).

If a patient is discontinued prematurely at any time after entering the study, the Investigator will make every effort to see the patient and complete an early termination visit.

The reason for any early discontinuation should be indicated on the termination page. The primary reason for a patient withdrawing prematurely should be selected from the following standard categories of early termination:

- **Medical decision:** Clinical or laboratory events occurred that in the medical judgment of the Investigator for the best interest of the patient are grounds for discontinuation. This includes serious and non-serious AEs regardless of relation to study medication.
- **Death:** The patient died.
- **Pregnancy:** The patient became pregnant.
- **Withdrawal of Consent:** The patient desired to withdraw from further participation in the study in the absence of an Investigator-determined medical need to withdraw. If the patient gave a reason for withdrawal, it should be recorded in the eCRF.
- **Lost to Follow-Up:** The patient stopped coming for visits, and study personnel were unable to contact the patient.
- **Other:** The patient was terminated for a reason other than those listed above, such as termination of the study by the Sponsor.

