10.9.13 Early Termination Visit

If the patient exits the study before Week 36 after having received at least one injection of study product, the following assessments and evaluations will be carried out whenever possible:

- Collect quality of life:
 - SF-36 health survey score
 - FACIT fatigue score
- Assess disease activity scores:
 - SLEDAI-2K
 - PGA
 - BILAG-2004 index
 - SELENA-SLEDAI flare index
 - SLICC/ACR-DI
 - Count of Tender & Swollen Joints
 - Joint Pain VAS
 - CLASI
- Record all AEs
- Record concomitant medication
- Perform complete physical examination, including body temperature and weight
- Measure vital signs – brachial pulse and blood pressure to be taken after 3 minutes of rest in a supine position

- Perform a gynecological examination, including examination of the cervix, cervical swabbing for cytological examination (PAP smear) and detection of high risk HPV (by RT qPCR)
- Perform a 12-lead ECG
- Obtain chest X-Ray where allowed by local regulation
- Perform urine pregnancy test for female patients of childbearing potential
- Perform urinalysis, including dipstick and microscopic examination
- Obtain blood sample for:
 - Hematology, coagulation (INR, PT, PTT, fibrinogen), biochemistry (complete)
 - Lymphocytes count (Total, CD4+, CD8+)
 - Anti-IFN α binding antibodies
 - Anti-KLH binding antibodies
 - Anti-IFN α neutralizing antibodies
 - Neutralizing Anti-IFN α antibodies towards IFN α subtypes
 - Anti-IFN α and anti-KLH antibody isotyping
 - IFN β cross-neutralization
 - Anti-dsDNA antibodies
 - ANA
 - Other autoantibodies (anti-Sm, anti-RNP, anti-SSA/Ro, anti-SSB/La, anti-cardiolipin and anti- β_2 -glycoprotein I antibodies)
 - Inflammatory markers (C3, C4, CH50)
 - IFN gene signature (by Affymetrix)

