11.6 SLE Disease Activity Assessment

The specific research instruments that will be used to assess disease activity and quality of life include:

- Chest X-Ray

Chest X-Ray will be obtained where allowed by Local Regulation for SLICC/ACR-DI purpose at Visit 2 (X-Ray obtained within previous month is acceptable) and at Visit 12.

- SLEDAI-2K score (Gladman *et al.*, 2002) - see Appendix 2

The SLEDAI scale measures disease activity. The original version was modified (SLEDAI-2K) to better reflect persistent active disease. There are 24 items in a total of 9 organs/systems; total scores range from 0 (non-active disease) – 105 points. Scores are attributed taking into account disease activity over the previous 10 days.

- BILAG-2004 index (Yee *et al.* 2010) - see Appendix 3

The BILAG 2004 index categorizes disease activity into 5 different levels from A–E, with Grade A representing very active disease and Grade E indicating no current or previous disease activity. Scoring is based on a total of 101 items, grouped into 9 organ/systems. Scores are attributed taking into account the signs/symptoms of SLE occurring over the previous 4 weeks.

- PGA score

PGA score is captured using 100 mm VAS

- SELENA-SLEDAI flare index (Petri *et al.*, 1999; Griffiths, *et al.* 2005) – see Appendix 4

- SLICC/ACR-DI (Gladman *et al.*, 1996) – see Appendix 5

The SLICC/ACR-DI captures permanent changes which have occurred in patients with SLE, regardless of causality. The questionnaire contains 41 items covering 12 different organ systems.

- Count of Tender and Swollen Joints and joint pain VAS – see Appendix 6

Count of Tender and Swollen Joints will be captured with 28-Tender and Swollen Joint counts and Joint pain is captured using 100 mm VAS

- CLASI (Albrecht *et al.*, 2005) – see Appendix 7

The CLASI was specifically developed to assess the cutaneous manifestations of SLE. It measures both disease activity and permanent damage (e.g. dyspigmentation and scarring) over the entire body surface.

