5.2.4.5 Exploratory analyses

The following analysis will be performed on the FAS population except if otherwise specified.

5.2.4.5.1 **PGA scores**

PGA score at each visit and change from baseline by treatment group will be presented. (Statistical tables 14.2.28.1 to 14.2.28.2)

All PGA data will be listed in Listing 16.2.6.10.

5.2.4.5.2 **SLE flares**

Time to first SLE flare in patients will be analyzed using a cox regression model.

The first model will be adjusted on treatment group.

The second model will be performed only on patients IFN-K treated and will be adjusted on presence/absence of neutralizing antibodies. (Statistical tables 14.2.29.1 to 14.2.29.2)

5.2.4.5.3 **28-Tender and Swollen Joint Counts (SJC)**

28-Tender and Swollen Joint Counts and Joint Pain VAS at each visit and change from baseline will be presented. The changes at Week 36 will be analyzed using a t-test. (Statistical tables 14.2.30.1 to 14.2.32.2).

28-Tender and Swollen joint counts data will be listed in Listing 16.2.6.11, and joint Pain VAS data in Listing 16.2.6.12.

5.2.4.5.4 **Treatment failure**

- Proportion of treatment failure will be analyzed using frequency table methods. Patients will be considered as treatment failure if they receive more than 5 mg prednisone equivalent/day at any time between Week 24 (Visit 9) and Week 36 (Visit 12) or if their CS dose is increased above the Week 24 level is recorded (this criterion will be identified by medical review) (Statistical table 14.2.33)

5.2.4.5.5 **SF-36**

Statistical Analysis Plan

Study Name: IFN-K-002

SAP version & date: v4, 18/Jun/2018

Physical Component Summary (PCS) and Mental Component Summary (MCS) scores at each visit and change from baseline will be presented. The changes at Week 36 will be analyzed using a non-parametric Wilcoxon rank sum test (Statistical tables 14.2.34.1 to 14.2.35.2). If one is statistically significant then the individual domain scores will also be described.

In addition, number of patients with clinically meaningful improvements \geq Minimum Clinically Important Differences (MCID) of 2.5 points for summary and 5.0 points for domain scores between baseline and Week 36 will be presented. (Statistical tables 14.2.36 to 14.2.37)

All SF-36 data will be presented in Listing 16.2.6.13.

5.2.4.5.6 **FACIT**

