7.5 LLDAS

Analysis for LLDAS, initially not planned in the protocol, will be done.

8 Software documentation

All summaries and statistical analyses will be generated using SAS version 9.4 or higher.

Statistical Analysis Plan

Study Name: IFN-K-002

SAP version & date: v4, 18/Jun/2018

9 Derived data

Derived variable	Derivation algorithm
Change from baseline to visit V (continuous)	
Change from baseline of variable X=X(Visit V)-X(Baseline)
 
 ○ Negative values indicate a decrease in X ○ Positive values indicate an increase in X
Percent change from baseline to visit V (continuous)	
Percent change from baseline of variable X=100 *[X(Visit V)-X(Baseline)]/X(Baseline)
 
 ○ Negative values indicate a decrease in X ○ Positive values indicate an increase in X
Treatment Compliance (continuous)	
The compliance Ci for patient i will be computed according to:
 $C_i = \frac{D_i^t * 100}{D_i^p}$ 
where D_i^p mg is the total amount (mg) of IP prescribed to patient i and D_i^t is the total amount (mg) of IP actually taken by the patient during the study i.e., before the end of study for patient i.

Treatment compliance (categorical) (if relevant)	
Categorial variable with three modalities:
 
 • $C_i < 80\%$ • $80\% \leq C_i < 120\%$ • $C_i \geq 120\%$
Event Duration	$(\text{End Date}) - (\text{Start Date}) + 1$
BILAG score	See BILAG-2004 Index scoring
SLEDAI-2K and SELENA SLEDAI	Sum of the weights
SLICC/ACR	Sum of items
CLASI	Sum of items
FACIT	See FACIT-Fatigue Subscale Scoring Guidelines (Version 4)

Statistical Analysis Plan

Study Name: IFN-K-002

SAP version & date: v4, 18/Jun/2018

Derived variable	Derivation algorithm
SF-36	See SF-36 Health Survey, Manual and Interpretation Guide
Time to event SLE flare	
SLE flare will be identified in BILAG-2004 scoring.
 
SLE flares are predefined as a BILAG A or B score due to items that were new or worse in any of the eight organ system (Isenberg et Al).
 
For patient with a SLE flare: Time to event = Visit date of corresponding BILAG – Date of Week 0 + 1
 
For patient without SLE flare: Time to event = Date of Week 36 (or date of end of study for patients prematurely withdrawn before Week 36) – Date of Week 0 +1

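### Time to first flare: patients with no closing BILAG are censored after their last BILAG, which adds flare-free time in which no flare could be recorded

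*SAP*

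**What the plan says.** SAP section 5.2.4.5.2, among the exploratory analyses on the FAS: "Time to first SLE flare in patients will be analyzed using a cox regression model". The outcome is derived in SAP section 9:

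- Source of events: "SLE flare will be identified in BILAG-2004 scoring".
- Event date: "Time to event = Visit date of corresponding BILAG", counted from Week 0 plus one day.
- No event: "Time to event = Date of Week 36 (or date of end of study for patients prematurely withdrawn before Week 36", counted in the same way.

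The SAP does not define the end-of-study date further, does not require a BILAG on it, and has no rule for missing BILAG visits in this analysis.

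The protocol provides a closing assessment. On premature discontinuation, section 10.6.2 says that "the Investigator will make every effort to see the patient and complete an early termination visit". Section 10.9.13 includes the BILAG-2004 index in that visit, but "the following assessments and evaluations will be carried out whenever possible". Section 10.6.2 also lists ways of leaving in which the visit may not happen: death, withdrawal of consent, and loss to follow-up ("The patient stopped coming for visits, and study personnel were unable to contact the patient"). Section 11.6 gives the BILAG look-back: "Scores are attributed taking into account the signs/symptoms of SLE occurring over the previous 4 weeks".

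**The concern.** Events and censoring run on different clocks. An event can occur only on a BILAG date, but censoring can fall on a later date with no BILAG. Between a patient's last BILAG and the end-of-study date, the patient is counted as at risk and flare-free although nobody looked for a flare. The same happens if a patient attends Week 36 but the BILAG is not done. A FAS patient with no post-baseline BILAG at all still contributes flare-free time.

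In a Cox model this matters only at another patient's flare date inside the gap: the unassessed patient is then in the risk set and inflates the denominator for his or her arm. If one arm has more such patients, its flare hazard looks too low. At stake is a small shift in an exploratory hazard ratio.

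**Working it through.** **1. Who is affected.** Set the detection rule beside the censoring rule for flare-free patients:

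| Patient | Last chance to record a flare | Censored at | Unassessed time |
|---|---|---|---|
| Completer with Week 36 BILAG | Week 36 | Week 36 | none |
| Withdrawn, early termination BILAG on the end-of-study date | that date | that date | none |
| Withdrawn, no early termination BILAG | last BILAG attended | end-of-study date | the gap |
| Attends Week 36, BILAG missing | last BILAG attended | Week 36 | the gap |

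Only the last two rows are a problem.

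**2. How many.** The plan gives no event count, hazard ratio or power for this analysis, so the only stated figure to reproduce is the drop-out allowance (protocol 13.1). 160 / 0.90 = 177.8, rounded up to 178, which matches. Expected drop-outs: 178 − 160 = 18. The third row is a subset of these.

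**3. One patient.** Suppose the last BILAG is at Week 20 and the end-of-study date is Week 28 (assumed).
- SAP rule: 28 × 7 + 1 = 197 days.
- Censoring at last BILAG: 20 × 7 + 1 = 141 days.
- Unassessed time: 56 days.

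**4. Total follow-up.** Take 160 completers at 36 weeks and 18 drop-outs leaving on average at Week 18 (assumed), ignoring that a flare ends follow-up: 160 × 36 + 18 × 18 = 6,084 patient-weeks. If all 18 lack a closing BILAG:
- gap 2 weeks: 18 × 2 = 36 (0.6%)
- gap 4 weeks: 72 (1.2%)
- gap 8 weeks: 144 (2.4%)
- gap 12 weeks: 216 (3.6%)

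If every early termination BILAG falls on the end-of-study date, the figure is 0.

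**5. Effect on the treatment hazard ratio.** Simulation with 89 per arm, BILAG every 4 weeks from Week 4 to Week 36 with a ±4-day window, true HR 1, Cox model with Efron ties, 400 runs per case. Assumptions not in the documents: flare probability per visit 5% or 10%; the withdrawal rates; the last BILAG of a withdrawn patient spread evenly over Weeks 4 to 32; the same gap for every withdrawn patient, capped at Week 36; no early termination BILAG on the end-of-study date. Entries are HR under the SAP rule divided by HR with censoring at the last BILAG (5% / 10% flare probability):

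| Withdrawal placebo / IFN-K | 2 weeks | 4 weeks | 8 weeks | 12 weeks |
|---|---|---|---|---|
| 10% / 10% | 1.000 / 1.000 | 1.000 / 0.999 | 1.000 / 1.001 | 1.002 / 0.999 |
| 5% / 15% | 0.995 / 0.994 | 0.988 / 0.988 | 0.977 / 0.976 | 0.969 / 0.965 |
| 5% / 25% | 0.989 / 0.989 | 0.975 / 0.975 | 0.952 / 0.952 | 0.933 / 0.935 |

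At true HR 1 the arms are interchangeable, so if placebo lost more patients the shift would go against IFN-K by a similar amount.

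**6. Scale.** With equal allocation the standard error of the log HR is roughly 2 / √events. In the 5% / 25%, 12-week case:
- 61 events: 2 / √61 = 0.256; ln 0.933 = −0.069; 0.069 / 0.256 = 0.27 SE.
- 102 events: 2 / √102 = 0.198; ln 0.935 = −0.067; 0.067 / 0.198 = 0.34 SE.

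In the 5% / 15%, 12-week case with 104 events: 2 / √104 = 0.196; ln 0.965 = −0.036; 0.036 / 0.196 = 0.18 SE.

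**The case against.** A reader might infer that every withdrawn patient adds time in which no flare could be found, and that the hazard ratio is therefore biased towards IFN-K. The documents do not support either step.

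- The early termination visit includes BILAG-2004, is planned for anyone leaving after at least one injection (the whole FAS), and the investigator must try hard to hold it. BILAG looks back 4 weeks, and no SAP rule excludes an early termination BILAG from flare detection.
- BILAG is scheduled every 4 weeks from Week 4, so a gap of 8 to 12 weeks means two or three missed visits and no closing visit. A patient with no post-baseline BILAG must leave very early and also miss the closing visit.
- Unequal withdrawal is not shown. Protocol 13.1 assumes one overall rate of 10%. Stopping the product is not withdrawal: patients are encouraged to continue procedures to Week 36 (10.6.3), and a missed injection does not lead to withdrawal (11.3). Both arms receive the same adjuvant. Lupus worsening scored as a flare on a BILAG before or at withdrawal is an event, not censored time.
- The endpoint is exploratory, outside the test sequence (SAP 5.3.5) and the success rule (SAP 5.2.4.1). The secondary SELENA-SLEDAI flare counts (SAP 5.2.4.3.4) do not use this clock.

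All of this stands, and it limits both who is affected and by how much. It does not remove the mismatch: the closing visit is not guaranteed, the protocol foresees patients who cannot be reached, and for them the stated rule counts unassessed time as flare-free.

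**Conclusion.** The point holds in a narrow form. For withdrawn, flare-free patients with no early termination BILAG, and for any flare-free patient whose Week 36 BILAG is missing, SAP section 9 adds follow-up in which no flare could be recorded. Where the early termination BILAG falls on the end-of-study date there is no effect.

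The treatment hazard ratio is essentially unchanged when withdrawal is balanced. If withdrawal differs, the ratio shifts in favour of the arm losing more patients, whichever arm that is: about 0.5% to 3.5% at 5% versus 15%, and up to about 7% at 5% versus 25% with a 12-week gap. The withdrawal rates, flare rates and gaps are assumptions. For those inputs the shifts are upper bounds, because no withdrawn patient was given an early termination BILAG. Even the largest is about a third of a standard error.

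The same derived time feeds the second Cox model, in IFN-K patients by neutralizing-antibody status. That model was not simulated, so the finding for balanced arms does not extend to it.

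This is a minor correction to a stated rule. It gives no reason to doubt the primary or secondary results.

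**What to change.** In the time-to-flare row of SAP section 9:

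- Censor flare-free patients at the date of their last BILAG up to Week 36 that is eligible for flare detection.
- State that an early termination BILAG counts for both event and censoring.
- Use an unscheduled BILAG for censoring only if it also counts for events. Under SAP 5.4.4 unscheduled data enter the analysis only if selected at the data review meeting. Censoring at a BILAG that could not count as an event would recreate the mismatch.
- Censor patients with no post-baseline BILAG at Day 1.

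This also covers a patient who attends Week 36 without a BILAG.

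Cost: a minor wording change and a small loss of follow-up time (0 to 216 of about 6,084 patient-weeks in the example above). No new data are needed. The change does not deal with informative drop-out, where patients who leave differ in flare risk from those who stay.

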10.1 List of tables

Number	Title	Screened	SAF	FAS	PP	Other
Demographics and Baseline characteristics						
14.1.1	Patient dispositions	X				
14.1.2.1	Datasets analyzed	X				
14.1.2.2	Reasons for exclusion from the FAS population		X			
14.1.2.3	Reasons for exclusion from the PP population			X		
14.1.3	Protocol deviations		X			
14.1.4	Demographics data		X	X		
14.1.5	Alcohol, drug and tobacco use			X		
14.1.6	Vital signs at baseline			X		
14.1.7	ECG at baseline			X		
14.1.8	Physical examination at baseline			X		
14.1.9	Hematology at baseline			X		
14.1.10	Chemistry at baseline			X		
14.1.11	Coagulation at baseline			X		
14.1.12	Urinalysis at baseline			X		
14.1.13	Hematology abnormalities at baseline			X		
14.1.14	Chemistry abnormalities at baseline			X		
14.1.15	Coagulation abnormalities at baseline			X		
14.1.16	Urinalysis abnormalities at baseline			X		
14.1.17	Viral serology at baseline			X		
14.1.18	Autoantibodies at baseline			X		
14.1.19	Inflammatory markers at baseline			X		
14.1.20	Gynecological examination			X		
14.1.21	Efficacy variables at baseline			X		
14.1.22	SLE medical history			X		
14.1.23	SLE flare history			X		
14.1.24	General Medical & Surgical history			X		
14.1.25	Permitted medications			X		
14.1.26	Prohibited medications			X		
14.1.27	Previous medications			X		
14.1.28	Compliance			X	X	
Efficacy						

Statistical Analysis Plan

Study Name: IFN-K-002

SAP version & date: v4, 18/Jun/2018

Number	Title	Screened	SAF	FAS	PP	Other
14.2.1.1.1	Primary efficacy analysis - First co-primary endpoint - Value at each visit			X		
14.2.1.1.2	Primary efficacy analysis - First co-primary endpoint - Change from baseline			X		
14.2.1.1.3	Primary efficacy analysis - First co-primary endpoint - ANCOVA model			X		
14.2.1.2.1	Primary efficacy analysis - Second co-primary endpoint - Response at Week 36			X		
14.2.1.2.2	Primary efficacy analysis - Second co-primary endpoint - Logistic regression model			X		
14.2.2.1.1	Primary efficacy analysis - First co-primary endpoint - Value at each visit				X	
14.2.2.1.2	Primary efficacy analysis - First co-primary endpoint - Change from baseline				X	
14.2.2.1.3	Primary efficacy analysis - First co-primary endpoint - ANCOVA model				X	
14.2.2.2.1	Primary efficacy analysis - Second co-primary endpoint - Response at Week 36				X	
14.2.2.2.2	Primary efficacy analysis - Second co-primary endpoint - Logistic regression model				X	
14.2.3.1.1	Primary efficacy analysis - First co-primary endpoint - Value at each visit					X
14.2.3.1.2	Primary efficacy analysis - First co-primary endpoint - Change from baseline					X
14.2.3.1.3	Primary efficacy analysis - First co-primary endpoint - ANCOVA model					X
14.2.3.1.4	Primary efficacy analysis - First co-primary endpoint - ANCOVA model - Covariates as randomized			X		
14.2.3.2.1	Primary efficacy analysis - Second co-primary endpoint - Response at Week 36					X
14.2.3.2.2	Primary efficacy analysis - Second co-primary endpoint - Logistic regression model					X
14.2.3.2.3	Primary efficacy analysis - Second co-primary endpoint - Logistic regression model - Covariates as randomized			X		
14.2.3.3.1	Primary efficacy analysis - First co-primary endpoint - ANCOVA model with status of IFN α neutralizing antibodies (positive/negative) at Week 36 as dependent variable			X		

Statistical Analysis Plan

Study Name: IFN-K-002

SAP version & date: v4, 18/Jun/2018

Number	Title	Screened	SAF	FAS	PP	Other
14.2.3.3.2	Primary efficacy analysis - Second co-primary endpoint - Logistic regression model with status of IFN α neutralizing antibodies (positive/negative) at Week 36 as dependent variable			X		
14.2.4	Sensitivity efficacy analysis - First co-primary endpoint - MMRM			X		
14.2.5.1	Secondary efficacy analysis - SRI-4 response at Week 36			X		
14.2.5.2	Secondary efficacy analysis - SRI-4 response - Logistic regression model			X		
14.2.5.3	Secondary efficacy analysis - SRI-4 response - Logistic regression model with status of IFN α neutralizing antibodies (positive/negative) at Week 36 as dependent variable				X	
14.2.5.4	Secondary efficacy analysis - SRI-4 response at Week 36				X	
14.2.5.5	Secondary efficacy analysis - SRI-4 response - Logistic regression model				X	
14.2.5.6	Secondary efficacy analysis - Composite SRI-4 response (CS 5 mg) at Week 36			X		
14.2.5.7	Secondary efficacy analysis - Composite SRI-4 response (CS 5 mg) - Logistic regression model			X		
14.2.5.8	Secondary efficacy analysis - Composite SRI-4 response (CS 5 mg) - Logistic regression model with status of IFN α neutralizing antibodies (positive/negative) at Week 36 as dependent variable				X	
14.2.5.9	Secondary efficacy analysis - Composite SRI-4 response (CS 7.5 mg) at Week 36			X		
14.2.5.10	Secondary efficacy analysis - Composite SRI-4 response (CS 7.5 mg) - Logistic regression model			X		
14.2.5.11	Secondary efficacy analysis - Composite SRI-4 response (CS 7.5 mg) - Logistic regression model with status of IFN α neutralizing antibodies (positive/negative) at Week 36 as dependent variable				X	
14.2.6.1	Secondary efficacy analysis - SRI-6 response at Week 36			X		
14.2.6.2	Secondary efficacy analysis - SRI-6 response at Week 36 - Logistic regression model			X		

Statistical Analysis Plan

Study Name: IFN-K-002

SAP version & date: v4, 18/Jun/2018

Number	Title	Screened	SAF	FAS	PP	Other
14.2.7.1	Secondary efficacy analysis - SRI-8 response at each visit			X		
14.2.7.2	Secondary efficacy analysis - SRI-8 response at Week 36 - Logistic regression model			X		
14.2.8.1	Secondary efficacy analysis - SRI-10 response at each visit			X		
14.2.8.2	Secondary efficacy analysis - SRI-10 response at Week 36 - Logistic regression model			X		
14.2.9	Secondary efficacy analysis - SLEDAI response at week 36			X		
14.2.10.1	Secondary efficacy analysis - SLEDAI-2K scores - Value at each visit			X		
14.2.10.2	Secondary efficacy analysis - SLEDAI-2K scores - Change from baseline			X		
14.2.11	Secondary efficacy analysis - BILAG - Shift table			X		
14.2.12	Secondary efficacy analysis - BILAG global score			X		
14.2.13	Secondary efficacy analysis - SELENA-SLEDAI - Mild, moderate or severe SLE flare			X		
14.2.14.1	Secondary efficacy analysis - SELENA-SLEDAI score - Value at each visit			X		
14.2.14.2	Secondary efficacy analysis - SELENA-SLEDAI score - Change from baseline			X		
14.2.15.1	Secondary efficacy analysis - SLICC/ACR-DI score - Value at each visit			X		
14.2.15.2	Secondary efficacy analysis - SLICC/ACR-DI score - Change from baseline			X		
14.2.16.1	Secondary efficacy analysis - CLASI - Total activity score - Value at each visit			X		
14.2.16.2	Secondary efficacy analysis - CLASI - Total activity score - Change from baseline			X		
14.2.17.1	Secondary efficacy analysis - CLASI - Total damage score - Value at each visit			X		
14.2.17.2	Secondary efficacy analysis - CLASI - Total damage score - Change from baseline			X		
14.2.18	Secondary efficacy analysis - LLDAS			X		
14.2.19	Immunogenicity analysis - Anti-IFN α binding antibody titers - Positive antibody response over time				X	
14.2.20	Immunogenicity analysis - Log-transformed dilution titers for anti-IFN α binding antibodies				X	

Statistical Analysis Plan

Study Name: IFN-K-002

SAP version & date: v4, 18/Jun/2018

Number	Title	Screened	SAF	FAS	PP	Other
14.2.21	Immunogenicity analysis - Anti-IFN α binding antibodies - GMT				X	
14.2.22	Immunogenicity analysis - Anti-IFN α antibody neutralizing capacity (NC50) - Positive antibody response over time				X	
14.2.23	Immunogenicity analysis - Log-transformed NC50 for anti-IFN α neutralizing antibodies				X	
14.2.24	Immunogenicity analysis - Anti-IFN α neutralizing antibodies - GMT				X	
14.2.25	Immunogenicity analysis - Anti-KLH binding antibody titers - Positive antibody response over time				X	
14.2.26	Immunogenicity analysis - Log-transformed dilution titers for anti-KLH binding antibodies				X	
14.2.27	Immunogenicity analysis - Anti-KLH binding antibodies - GMT				X	
14.2.28.1	Exploratory analysis - PGA score - Value at each visit			X		
14.2.28.2	Exploratory analysis - PGA score - Change from baseline			X		
14.2.29.1	Exploratory analysis - SLE Flare - Cox model adjusted on treatment group			X		
14.2.29.2	Exploratory analysis - SLE Flare - Cox model adjusted on presence/absence of neutralizing antibodies			X		
14.2.30.1	Exploratory analysis - 28-Tender joints counts - Value at each visit			X		
14.2.30.2	Exploratory analysis - 28-Tender joints counts - Change from baseline			X		
14.2.31.1	Exploratory analysis - 28-Swollen joints counts - Value at each visit			X		
14.2.31.2	Exploratory analysis - 28-Swollen joints counts - Change from baseline			X		
14.2.32.1	Exploratory analysis - Joint Pain VAS - Value at each visit			X		
14.2.32.2	Exploratory analysis - Joint Pain VAS - Change from baseline			X		
14.2.33	Exploratory analysis - Treatment failure			X		
14.2.34.1	Exploratory analysis - SF-36 - Physical Component Summary (PCS) - Value at each visit			X		
14.2.34.2	Exploratory analysis - SF-36 - Physical Component Summary (PCS) - Change from baseline			X		

Statistical Analysis Plan

Study Name: IFN-K-002

SAP version & date: v4, 18/Jun/2018

Number	Title	Screened	SAF	FAS	PP	Other
14.2.35.1	Exploratory analysis - SF-36 - Mental Component Summary (MCS) - Value at each visit			X		
14.2.35.2	Exploratory analysis - SF-36 - Mental Component Summary (MCS) - Change from baseline			X		
14.2.36	Exploratory analysis - Clinically meaningful improvements - Physical Component Summary (PCS)			X		
14.2.37	Exploratory analysis - Clinically meaningful improvements - Mental Component Summary (MCS)				X	
14.2.38	Exploratory analysis - Clinically meaningful improvements - Domains			X		
14.2.39.1	Exploratory analysis - FACIT total score - Value at each visit				X	
14.2.39.2	Exploratory analysis - FACIT total score - Change from baseline			X		
14.2.40.1	Exploratory analysis - Autoantibodies - Value at each visit				X	
14.2.40.2	Exploratory analysis - Autoantibodies - Change from baseline				X	
14.2.41.1	Exploratory analysis - Biomarkers - Value at each visit				X	
14.2.41.2	Exploratory analysis - Biomarkers - Change from baseline				X	
14.2.42	Exploratory analysis - Anti-IFN α and anti-KLH antibody isotyping				X	
14.2.43	Exploratory analysis - Anti-Hemagglutinin antibody response following influenza vaccination				X	
14.2.44	Exploratory analysis - Neutralizing Anti-IFN α antibodies towards IFN α subtypes				X	
14.2.45.1	Correlation - Qualitative description for clinical parameters at V12 by status of neutra at V12 on patients treated with IFN-K and with positive binding at V12					X
14.2.45.2	Correlation - Quantitative or qualitative description for biological parameters at V12 by treatment group on patients responder for BICLA at V12					X
14.2.45.3	Correlation - Quantitative or qualitative description for biological parameters at V12 by treatment group on patients non responder for BICLA at V12					X

Statistical Analysis Plan

Study Name: IFN-K-002

SAP version & date: v4, 18/Jun/2018

Number	Title	Screened	SAF	FAS	PP	Other
14.2.45.4	Correlation - Quantitative or qualitative description for biological parameters at V12 by treatment group on patients responder for SRI4 at V12				X	
14.2.45.5	Correlation - Quantitative or qualitative description for biological parameters at V12 by treatment group on patients non responder for SRI4 at V12				X	
14.2.45.6	Correlation - Quantitative or qualitative description for biological parameters at V12 by status of neutral at V12 on patients patients treated with IFN-K and with positive binding at V12				X	
Safety						
14.3.1	Extent of exposure		X			
14.3.2	Summary of Adverse events		X			
14.3.3.1	Solicited local reactions during a 7-day follow-up period after each study product administration by SOC and PT - Period [1st dose; 2nd dose[X			
14.3.3.2	Solicited local reactions during a 7-day follow-up period after each study product administration by SOC and PT - Period [2nd dose; 3rd dose[X			
14.3.3.3	Solicited local reactions during a 7-day follow-up period after each study product administration by SOC and PT - Period [3rd dose; 4th dose[X			
14.3.3.4	Solicited local reactions during a 7-day follow-up period after each study product administration by SOC and PT - Period [4th dose; 5th dose[X			
14.3.3.5	Solicited local reactions during a 7-day follow-up period after each study product administration by SOC and PT - Period [5th dose; Week 36]		X			
14.3.3.6	Solicited local reactions during a 7-day follow-up period after each study product administration by SOC and PT - Period [Last dose;Week 36/Early Termination]		X			
14.3.4.1	Solicited local reactions during a 7-day follow-up period after each study product administration by SOC, PT and intensity - Period [1st dose; 2nd dose[X			
14.3.4.2	Solicited local reactions during a 7-day follow-up period after each study product administration by SOC, PT and intensity - Period [2nd dose; 3rd dose[X			

Statistical Analysis Plan

Study Name: IFN-K-002

SAP version & date: v4, 18/Jun/2018

Number	Title	Screened	SAF	FAS	PP	Other
14.3.4.3	Solicited local reactions during a 7-day follow-up period after each study product administration by SOC, PT and intensity - Period [3rd dose; 4th dose[X			
14.3.4.4	Solicited local reactions during a 7-day follow-up period after each study product administration by SOC, PT and intensity - Period [4th dose; 5th dose[X			
14.3.4.5	Solicited local reactions during a 7-day follow-up period after each study product administration by SOC, PT and intensity - Period [5th dose; Week 36]		X			
14.3.4.6	Solicited local reactions during a 7-day follow-up period after each study product administration by SOC, PT and intensity - Period [Last dose; Week 36/Early Termination]		X			
14.3.5.1	Solicited systemic reactions during a 7-day follow-up period after each study product administration by SOC and PT - Period [1st dose; 2nd dose[X			
14.3.5.2	Solicited systemic reactions during a 7-day follow-up period after each study product administration by SOC and PT - Period [2nd dose; 3rd dose[X			
14.3.5.3	Solicited systemic reactions during a 7-day follow-up period after each study product administration by SOC and PT - Period [3rd dose; 4th dose[X			
14.3.5.4	Solicited systemic reactions during a 7-day follow-up period after each study product administration by SOC and PT - Period [4th dose; 5th dose[X			
14.3.5.5	Solicited systemic reactions during a 7-day follow-up period after each study product administration by SOC and PT - Period [5th dose; Week 36]		X			
14.3.5.6	Solicited systemic reactions during a 7-day follow-up period after each study product administration by SOC and PT - Period [Last dose; Week 36/Early Termination]		X			
14.3.6.1	Solicited systemic reactions during a 7-day follow-up period after each study product administration by SOC, PT and intensity - Period [1st dose; 2nd dose[X			
14.3.6.2	Solicited systemic reactions during a 7-day follow-up period after each study product administration by SOC, PT and intensity - Period [2nd dose; 3rd dose[X			
14.3.6.3	Solicited systemic reactions during a 7-day follow-up period after each study product administration by SOC, PT and intensity - Period [3rd dose; 4th dose[X			

Statistical Analysis Plan

Study Name: IFN-K-002

SAP version & date: v4, 18/Jun/2018

Number	Title	Screened	SAF	FAS	PP	Other
14.3.6.4	Solicited systemic reactions during a 7-day follow-up period after each study product administration by SOC, PT and intensity - Period [4th dose; 5th dose[X			
14.3.6.5	Solicited systemic reactions during a 7-day follow-up period after each study product administration by SOC, PT and intensity - Period [5th dose; Week 36]		X			
14.3.6.6	Solicited systemic reactions during a 7-day follow-up period after each study product administration by SOC, PT and intensity - Period [Last dose; Week 36/Early Termination]		X			
14.3.7.1	TEAEs by SOC and PT - Period [1st dose; 2nd dose[X			
14.3.7.2	TEAEs by SOC and PT - Period [2nd dose; 3rd dose[X			
14.3.7.3	TEAEs by SOC and PT - Period [3rd dose; 4th dose[X			
14.3.7.4	TEAEs by SOC and PT - Period [4th dose; 5th dose[X			
14.3.7.5	TEAEs by SOC and PT - Period [5th dose; Week 36]		X			
14.3.7.6	TEAEs by SOC and PT - Period [Last dose; Week 36/Early Termination]		X			
14.3.7.7	TEAEs by SOC, PT and status of anti-IFN α neutralizing antibodies and anti-IFN α binding antibodies at time of event - Period [3rd dose; 4th dose[X			
14.3.7.8	TEAEs by SOC, PT and status of anti-IFN α neutralizing antibodies and anti-IFN α binding antibodies at time of event - Period [4th dose; 5th dose[X			
14.3.7.9	TEAEs by SOC, PT and status of anti-IFN α neutralizing antibodies and anti-IFN α binding antibodies at time of event - Period [5th dose; Week 36]		X			
14.3.7.10	TEAEs by SOC, PT and status of anti-IFN α neutralizing antibodies and anti-IFN α binding antibodies at time of event - Period [Last dose; Week 36/Early Termination]		X			
14.3.8.1	TEAEs by SOC, PT and relationship - Period [1st dose; 2nd dose[X			
14.3.8.2	TEAEs by SOC, PT and relationship - Period [2nd dose; 3rd dose[X			
14.3.8.3	TEAEs by SOC, PT and relationship - Period [3rd dose; 4th dose[X			

Statistical Analysis Plan

Study Name: IFN-K-002

SAP version & date: v4, 18/Jun/2018

Number	Title	Screened	SAF	FAS	PP	Other
14.3.8.4	TEAEs by SOC, PT and relationship - Period [4th dose; 5th dose[X				
14.3.8.5	TEAEs by SOC, PT and relationship - Period [5th dose; Week 36]	X				
14.3.8.6	TEAEs by SOC, PT and relationship - Period [Last dose; Week 36/Early Termination]	X				
14.3.9.1	TEAEs by SOC, PT and intensity - Period [1st dose; 2nd dose[X				
14.3.9.2	TEAEs by SOC, PT and intensity - Period [2nd dose; 3rd dose[X				
14.3.9.3	TEAEs by SOC, PT and intensity - Period [3rd dose; 4th dose[X				
14.3.9.4	TEAEs by SOC, PT and intensity - Period [4th dose; 5th dose[X				
14.3.9.5	TEAEs by SOC, PT and intensity - Period [5th dose; Week 36]	X				
14.3.9.6	TEAEs by SOC, PT and intensity - Period [Last dose; Week 36/Early Termination]	X				
14.3.10	TEAEs leading to permanent study drug discontinuation by SOC and PT	X				
14.3.11.1	SAEs by SOC and PT - Before 1st dose	X				
14.3.11.2	SAEs by SOC and PT - Period [1st dose; 2nd dose[X				
14.3.11.3	SAEs by SOC and PT - Period [2nd dose; 3rd dose[X				
14.3.11.4	SAEs by SOC and PT - Period [3rd dose; 4th dose[X				
14.3.11.5	SAEs by SOC and PT - Period [4th dose; 5th dose[X				
14.3.11.6	SAEs by SOC and PT - Period [5th dose; Week 36]	X				
14.3.11.7	SAEs by SOC and PT - Period [Last dose; Week 36/Early Termination]	X				
14.3.11.8	SAEs by SOC, PT and status of IFN α neutra (positive/negative) at time of event - Period [3rd dose; 4th dose[X				
14.3.11.9	SAEs by SOC, PT and status of IFN α neutra (positive/negative) at time of event - Period [4th dose; 5th dose[X				
14.3.11.10	SAEs by SOC, PT and status of IFN α neutra (positive/negative) at time of event - Period [5th dose; Week 36]	X				
14.3.11.11	SAEs by SOC, PT and status of IFN α neutra (positive/negative) at time of event - Period [Last dose; Week 36/Early Termination]	X				

Confidential

Statistical Analysis Plan

Study Name: IFN-K-002

SAP version & date: v4, 18/Jun/2018

Number	Title	Screened	SAF	FAS	PP	Other
14.3.12.1	SAEs by SOC, PT and relationship - Before 1st dose	X				
14.3.12.2	SAEs by SOC, PT and relationship - Period [1st dose; 2nd dose[X			
14.3.12.3	SAEs by SOC, PT and relationship - Period [2nd dose; 3rd dose[X			
